The present study will be a single-center, double-blinded, parallel-group, randomized, placebo-controlled trial. Figure 1 illustrates the study design. Initially, participants will be pre-screened through phone calls or personal interviews. Those who meet the preliminary criteria will then be further assessed for their medical condition and eligibility criteria. Eligible participants will be matched based on sex and then randomly allocated in a 1:1:1 ratio into one of the following experimental groups: (a) protein supplementation (PTN), (b) placebo supplementation (PLA), or (c) control (CON). Both the PTN and PLA groups will receive dietary supplementation, will be caloric-restricted, and will engage in an exercise training program. Participants in the CON group will receive no intervention other than general guidance on healthy eating and physical activity. All outcomes of interest will be assessed immediately before participants' randomization at baseline (PRE) and after 16 weeks of intervention (POST). Anthropometric and dietary parameters will be reassessed at weeks 4, 8, and 12. Participants will also meet with a registered dietitian from the research team every two weeks in order to ensure compliance with the dietary intervention.

RANDOMIZATION

Eligible participants will be sex-matched and then randomly allocated using a computer-generated block design in a 1:1:1 ratio into one of the following experimental groups through a specific software (<https://randomizer.org>): (a) protein supplementation (PTN), (b) placebo supplementation (PLA), or (c) control (CON). The allocation sequence will be concealed from the research staff.

EXAMINATIONS

The primary outcome will be the change from baseline in fat-free mass (total, appendicular, appendicular relative to BMI and leg). Secondary outcomes will include other measures of body composition (i.e. fat and bone density), bone microarchitecture, bone metabolism, and specific muscle functions. Other outcomes, including cardiopulmonary capacity (cardiorespiratory fitness and pulmonary function), glycemic control, insulin sensitivity, endothelial function, inflammation, cognitive function and

related cellular and molecular mechanisms (telomere length, oxidative stress, and lipid profile) will also be assessed.

Anthropometry

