Sample size was determined a priori using the G-Power software (Version 3.1.9.2, University of Kiel, Germany). The analysis was conducted by inputting α error (0.05), power ($1 - \beta$ error = 0.95), and effect size (Hedges' g = 0.61), considering previous data indicating a lower loss of fat-free mass in individuals undergoing caloric restriction who had an increase in protein intake compared to their counterparts who maintained their usual protein intake (31). Calculations were based on an ANOVA with repeated measures (within-between interactions) and the total sample size was determined to be 81 individuals. To account for midtrial withdrawals, the sample will be increased by ~30% (i.e. 105 participants).

DATA ANALYSIS

Data will be presented as mean \pm standard deviation (SD), estimated mean difference between groups (EMD) at POST (only in the presence of group x time interaction), 95% confidence interval (95%CI), unless otherwise indicated. Baseline characteristics will be compared between groups using either Fisher exact test or generalized linear model with Sidak post hoc adjustment whenever necessary. Data will be analyzed using an intention-to-treat (ITT) approach to preserve the integrity of randomization. Before inferential analysis, outliers will be identified, and the data will be tested for homogeneity of variance and sphericity. Dependent variables will be analyzed by a linear mixed model analysis for repeated measures (assuming time [PRE and POST] and group [PTN, and PLA] with baseline values as covariate. The restricted maximum likelihood method, compound symmetry covariance structure, and Kenward-Roger degrees of freedom approximation will be applied for all models. In order to maintain the overall significance level at 0.05, the primary endpoints will be assessed using Hochberg's procedure (124). For all secondary outcomes the significance level will be set at $p \leq 0.05$. Whenever significant group-by-time interactions are identified, post-hoc tests on the adjusted predictions with Sidak's adjustment will be performed for multiple comparisons.

All analyses will be performed in the statistical environment R (version 3.5.3; R Core Team 2020).

STATISTICAL ANALYSIS PLAN

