All analyses will be performed in the statistical environment R (version 3.5.3; R Core Team 2020). We will perform all the comparisons using two-sided significance tests. Intention-to-treat analyses will be performed by analyzing data from all participants originally randomized to preserve the integrity of randomization. The longitudinal analysis of all outcomes will be performed using a linear mixed model for repeated measures, assuming 'group' (PTN, and PLA) and 'time' (pre-intervention and post-intervention) as fixed factors, and 'subjects' as a random factor, with an interaction between 'group' and 'time' added to the model; baseline values of the outcome will be used as covariates. For all models, maximum restricted likelihood and Kenward-Roger degrees of freedom will be used for model fit and estimation. We will adjust for testing of the four primary outcomes, total fat-free mass, appendicular fat-free mass, appendicular fat-free mass relative to body mass index, and leg fat-free mass, using Hochberg's procedure in order to maintain the overall significance level at 0.05. Since the other hypothesis tests (for the secondary outcomes) will be more exploratory in nature, the Hochberg's correction will not be used, and two-sided p-values less than 0.05 will be considered to indicate statistical significance. For both primary and secondary outcomes, whenever significant group-by-time interactions are identified, post-hoc tests on the adjusted predictions with Sidak's adjustment will be performed for multiple comparisons.

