Mixed model analyses will be used instead of standard repeated measures analysis of variance because of the likelihood that there will be dropouts and missed visits that preclude the use of the classical approach (125, 126). The mixed model approach we will employ fits a linear regression model to each subject and assumes that both error terms and regression coefficients are normally distributed in these lines. It then uses the EM algorithm to combine the individual lines and to generate empirical Bayes, maximum likelihood, and restricted maximum likelihood estimates of model parameters. Because lines are generated for individuals, the model is more general than standard repeated measures analysis of variance in that it has no requirements about common measurement times between subjects and can deal easily with missing data. In all analyses, careful attention will be given to ensuring that the conditions that are required of a particular statistical method are satisfied. We will assess the normality of regression residuals and ensure the homogeneity of variances when analyzes of variance and covariance are performed. When required assumptions are not satisfied, data transformations will be explored and utilized as appropriate.

STUDY TIME LINE

July 2021 – August 2023

REFERENCES

1. Roh E, Choi KMJFie. Health consequences of sarcopenic obesity: a narrative review. 2020;11:530178.
2. Wannamethee SG, Atkins JLJCDR. Sarcopenic obesity and cardiometabolic health and mortality in older adults: a growing health concern in an ageing population. 2023;23(11):307-14.

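### The SAP describes a line-per-subject mixed model that two visits cannot estimate and that contradicts the compound-symmetry model stated before it; that model is not a safe fallback under dropout

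*Combined protocol and SAP*

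**What the plan says.** Three places in the combined protocol and SAP bear on the model for the four fat-free mass outcomes.

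- **Data Analysis** sets a linear mixed model with time at PRE and POST and the baseline value as covariate. It adds that the "compound symmetry covariance structure, and Kenward-Roger degrees of freedom approximation will be applied for all models".
- **Statistical Analysis Plan, first paragraph**, covers all outcomes. It takes "time' (pre-intervention and post-intervention) as fixed factors, and 'subjects' as a random factor", adds the group-by-time interaction, and again uses the baseline value as covariate.
- **Statistical Analysis Plan, second paragraph**, justifies mixed models by expected dropouts and missed visits. It then says that the approach to be employed "fits a linear regression model to each subject and assumes that both error terms and regression coefficients are normally distributed". It continues: "It then uses the EM algorithm to combine the individual lines and to generate empirical Bayes, maximum likelihood, and restricted maximum likelihood estimates". It claims as an advantage that "it has no requirements about common measurement times between subjects and can deal easily with missing data".

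Under Study Design, the outcomes are assessed "at baseline (PRE) and after 16 weeks of intervention (POST"). Weeks 4, 8 and 12 add anthropometry and diet only. The follow-up procedure asks a participant who drops out for a full examination at that time, so there are still at most two fat-free mass values per person.

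**The concern.** A line per subject with normally distributed coefficients (in the plural) plus a normally distributed error is a random-intercept, random-slope model. Two points fix a line exactly, so nothing is left from which to separate slope variation from residual error. Random slopes also let the variance change with time, which compound symmetry rules out.

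The paragraph is written as the model that will be employed, so the analyst has to set aside part of the plan once data are in hand. The natural retreat is the random-subject model with baseline as covariate. That model carries its own problem, because the PRE value appears on both sides of the equation.

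**Working it through.** The plan gives no figure for this point, so there is none to reproduce. SDs, correlations and dropout mechanisms below are assumptions.

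**1. Counting parameters.** Let τ0², τ1² and τ01 be the intercept variance, slope variance and their covariance, and σ² the residual variance. With visits at 0 and 16 weeks:

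- Var(PRE) = τ0² + σ²
- Cov(PRE, POST) = τ0² + 16τ01
- Var(POST) = τ0² + 32τ01 + 256τ1² + σ²

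That is four unknowns in three equations, and the mapping has rank 3. With three or five visits the rank is 4. A random intercept alone has two parameters and rank 2 at two visits, so its variances are identified.

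**2. Same covariance, different parameters.** Assume Var(PRE) = 36, Var(POST) = 37 and covariance 34.

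| σ² | τ0² | τ01 | τ1² |
|---|---|---|---|
| 0 | 36.0 | -0.125 | 0.01953 |
| 0.5 | 35.5 | -0.09375 | 0.01562 |
| 1.0 | 35.0 | -0.0625 | 0.01172 |
| 1.4 | 34.6 | -0.0375 | 0.00859 |

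All four rows return the assumed matrix. For σ² = 1.0: PRE 35 + 1 = 36; covariance 35 - 1 = 34; POST 35 - 2 + 3 + 1 = 37.

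**3. Fitting it.** In simulated two-visit data (35 per arm, no baseline covariate) the REML log-likelihood was -360.0428 at residual variances 0.01, 0.3, 0.6, 1.0 and 1.3 alike. In R, lme4 refused the random-slope model on 70 subjects at two visits: 140 observations against 140 random effects.

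**4. What survives.** In the REML data of step 3, the group-by-time estimate was 0.469 (SE 0.492) under a random intercept, at every point on the flat ridge, and in a t-test on change scores.

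**5. The random-subject model with PRE as both outcome and covariate.** Take SD 6 kg and correlation 0.95. The estimated subject variance is often zero (63 to 96% of simulated fits across settings). The pooled baseline coefficient then sits near (1 + 0.95)/2 = 0.975, and the residual variances are about:

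- PRE: (1 - 0.975)² × 36 = 0.0225
- POST: 36 × (1 - 0.95²) + (0.95 - 0.975)² × 36 = 3.51 + 0.0225 = 3.5325

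The model assumes that these are equal.

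- Complete data, 35 per arm: pooled variance (0.0225 + 3.5325)/2 = 1.7775, so SE = √(1.7775 × 4/35) = 0.451. The change-score SE is √(2 × 36 × 0.05 × 2/35) = 0.454. These agree.
- Dropout of 8 per arm (8/35 = 23%, the same as (105 - 81)/105): pooled variance (35 × 0.0225 + 27 × 3.5325)/62 = 1.551, so SE = √(1.551 × (2/35 + 2/27)) = 0.451. The actual sampling SD is about √(2 × 3.5325/27) = 0.512.

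The reported SE does not grow as POST values are lost. The ratio is 0.451/0.512 = 0.881, so a nominal 1.96 cut-off behaves like 1.73, a two-sided error of about 8%.

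**6. Simulation under no effect, 35 per arm, 23% random dropout.**

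- 1,500 runs per setting, t-test on completers minus 2 degrees of freedom: the random-subject model had type I error 9.3% (correlation 0.95; mean SE 0.452, true SD 0.524) and 9.4% (0.80). An unstructured 2x2 covariance without the baseline covariate gave 4.8% and 5.0%.
- A check with separate code, 3,000 runs per setting: random-subject 8.0% and 8.6%; POST on group and baseline 4.6% and 5.4%.
- Without dropout, all of these models lay between 4.5% and 5.5% in both simulations.

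**7. A trap in the remedy.** If an unstructured covariance is used and the baseline covariate is kept, PRE is predicted perfectly. As the PRE residual variance was set to 1, 0.01, 1e-4, 1e-6 and 1e-8, the REML log-likelihood rose through -162, -45, 73, 190 and 308, without bound.

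**The case against.** The best defence is that Data Analysis and the first SAP paragraph are the operative text, and the second paragraph is a generic account of mixed models that names no slope term, time variable or covariance structure. Much of this stands. A random subject effect implies compound symmetry, so those two statements describe one model whose variance parameters are identified. The lead reason for a mixed model, expected dropout, remains valid.

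Four stronger readings are tempting and not supported:

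- *Three rival covariance models.* There are two: the random-subject, compound-symmetry model and the individual-lines model.
- *A random subject effect on top of a compound-symmetry residual, counting the same covariance twice.* Nothing in the plan asks for that combination.
- *The case for a mixed model collapses.* Only the remarks on individual lines and measurement times fail to fit a two-level time factor.
- *The primary result is biased.* The treatment effect remains estimable; only the split between slope and residual variance is lost.

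Reading the lines as parallel, with random intercepts only, would remove the conflict, but the wording does not say so. Drop-out examinations entered at their actual dates could identify a slope variance in principle. That would rest on the drop-outs alone, and the SAP makes time a two-level factor. Those examinations could also reduce missingness, but the SAP does not say how they enter the model.

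**Conclusion.** The point holds as a defect of specification. The individual-lines model cannot be estimated for outcomes modelled at two visits (four parameters, three moments, whatever the SD or correlation), and it contradicts the compound-symmetry model set for all analyses. With complete data the group-by-time result is practically the same under the fittable models.

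The random-subject model as written is not a safe fallback. With dropout at the level the sample size allows for, its type I error was roughly 8 to 10% against a nominal 5%. That figure rests on an assumed SD of 6 kg, correlations of 0.80 and 0.95, 35 per arm, dropout at random, and degrees of freedom simpler than Kenward-Roger. It would shrink towards nominal as dropout falls. It illustrates the risk and does not predict this trial's error rate. The plan should be corrected on this point.

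**What to change.** Delete the SAP text on individual lines, the EM algorithm and common measurement times. Keep the sentence on dropouts if a mixed model is retained. State one model, in the same words in Data Analysis and the Statistical Analysis Plan, for all four primary outcomes:

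- POST regressed on group and the baseline value; or
- if PRE stays in the response, group, time and their interaction with an unstructured 2x2 covariance, REML and Kenward-Roger, and **no** baseline covariate.

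State also how a drop-out examination enters the analysis.

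The cost is wording only, with no new data. The first option leaves out participants with no POST value, which must be squared with the SAP's commitment to analyse everyone randomised. Under dropout the reported SE will be somewhat larger than from the current model (mean 0.514 against 0.449 at correlation 0.95 in the 3,000-run check), which reflects the information actually lost.
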